2.3 Study Rationale

The rationale for the proposed research is to develop an acute intervention that can improve treatment outcomes in OUD by reducing craving, a primary factor contributing to early relapse. Although liraglutide was approved for human use in 2010, there are no data testing the effectiveness in patients with an OUD. The objective of the proposed research is to test whether treatment with a GLP-1R agonist can reduce craving in humans with OUD. Understanding how a 'satiety' agent may affect craving and brain responses to drug cues in an OUD population would provide entirely novel information. If liraglutide shows a trend towards efficacy, and safety of the GLP-1R agonist is demonstrated in this population, it would provide an indication to run the second phase, multi-center clinical trial of GLP-1R agonist in OUD patients.

3.0 Inclusion and Exclusion Criteria

3.1 Inclusion Criteria

To be eligible to participate in this study, candidates must meet the following eligibility criteria at screening:

- 1. Age 18 to 75 years
- 2. Diagnosed with an OUD seeking treatment at Caron Treatment Centers (CaronTC) and planning on being enrolled in a residential treatment plan for a minimum of 4 weeks
- 3. Women of childbearing potential must consent to use a medically accepted method of birth control or to abstain from sexual intercourse while in the study
- 4. Able and willing to provide informed consent prior to any study-related activities
- 5. Must be able to read and communicate in English sufficiently to complete all study requirements, including EMA

3.2 Exclusion Criteria

Patients will be excluded from study entry if any of the following exclusion criteria exist at screening:

- 1. Age < 18 or > 75 years
- 2. Women who are pregnant, planning pregnancy, breastfeeding, or unwilling to use adequate contraceptive measures
- 3. History of angioedema, serious hypersensitivity reaction, or anaphylactic reaction to liraglutide or another glucagon-like peptide-1 receptor (GLP1R) agonist
- 4. Personal or family history of medullary thyroid carcinoma (MTC) or patients with multiple endocrine neoplasia syndrome type 2 (MEN 2) or thyroid nodule
- 5. Type I diabetes or history of diabetic ketoacidosis
- 6. Type II diabetes mellitus
- 7. Hypoglycemia on intake visit (blood glucose < 70 mg/dL)
- 8. End-stated renal failure on dialysis **or** glomerular filtration rate (GFR) <30mL/min per 1.73 square meters **or** previous renal transplant
- 9. Severe hepatic impairment (AST or ALT levels > 3 times upper limit of normal range) or previous liver transplant
- 10. Current or past diagnosis of pancreatitis, gastroparesis, or other severe gastrointestinal disease
- 11. Current or past diagnosis of gallbladder disease or gallstones
- 12. Serious cardiovascular disease within the past 6 months (e.g. uncontrolled hypertension, heart failure, significant cardiac arrhythmias, myocardial infarction, presence of angina pectoris, symptomatic coronary artery disease, deep vein thrombosis, pulmonary embolism, second- or third-degree heart block, mitral valve or aortic stenosis, hypertrophic cardiomyopathy, stroke)

- 13. Severe co-occurring psychiatric disorder (e.g., bipolar disorder, psychotic disorder, schizophrenia) that would, in the opinion of the Principle Investigator or study physician, interfere with participating in the study, such as if the patient needs a higher or different level of care and is going to be transferred out of Caron.
- 14. Suicidal ideation within the past 1 month, or history of suicide attempts within the past 1 year, unless participation is cleared by clinician assessment and/or judgement.
- 15. Treatment with any investigational drug in the one-month preceding the study
- 16. Previous randomization for participation in this trial
- 17. Abnormal physical exam findings, vital signs (blood pressure, heart rate, respiratory rate, body temperature), EKG measurements, and safety lab values that are deemed clinically significant by study physician

3.3 Early Withdrawal of Subjects

3.3.1 Criteria for removal from study

Blood pressure, heart rate, and respiratory rate will be measured on Days 1, 2, 8, 14, 19, and 21. On each day, each measure will be recorded 3-4 times and then averaged. Participants will be withdrawn if they experience an average daily value for any measure on Day 1, 2, 8, 14, or 19:

- Systolic blood pressure (SBP) changes >40 mmHg, or SBP <90 mmHg or >200 mmHg, or clinical symptoms of hypertension (e.g. headache, dizziness, blurred vision, nausea edema) or hypotension (e.g. dizziness, nausea, fainting) develop
- Heart rate reaches levels <40 beats/min or >120 beats/min
- Respiratory rate changes by >5 breaths/minute or reaches levels <10 breaths/minute or >24 breaths/minute

The investigators will also exercise discretion to end an individual's study participation if they should engage in behavior that could jeopardize their own health and well-being or that of others

Participants who develop any new conditions described in the exclusion criteria during the treatment phase of clinical trial will be removed from the study

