1.3 Secondary Study Endpoints

The secondary objective of this pilot study is to evaluate the safety of daily administration of liraglutide in humans seeking treatment for an OUD.

1) Cardiorespiratory Function

- a. *Blood Pressure*. Change in blood pressure from baseline (Day 1) to: i) the beginning of each study drug dose (Days 2, 8, 14, 20, 26); ii) end of the target drug dose (Day 19 [Day 31 for 5-dose intervention]); and iii) rebound follow-up (Day 21 [Day 33 for 5-dose intervention]).
- b. Heart Rate. Change in heart rate from baseline (Day 1) to: i) the beginning of each study drug dose (Days 2, 8, 14, 20, 26); ii) end of the target drug dose (Day 19, [Day 31 for 5-dose intervention]); and iii) rebound follow-up (Day 21 [Day 33 for 5-dose intervention]).
- c. *Respiration*. Change in respiratory from baseline (Day 1) to: i) the beginning of each study drug dose (Days 2, 8, 14, 20, 26); ii) end of the target drug dose (Day 19 [Day 31 for 5-dose intervention]); and iii) rebound follow-up (Day 21 [Day 33 for 5-dose intervention]).

- 2) **Body Weight** (*kg*). Absolute and percent change in body weight from baseline through the end of rebound follow-up (Daily, from Days 1 to 21 [Days 1-33 for 5-dose intervention]).
- 3) **Glycemic Control.** Glycemic control will be monitored by fasting blood samples for fructosamine and A1c. Fasting blood sample measurements change slowly overtime (i.e., across weeks and months) and therefore will be evaluated only on Days 2 and 19 [and additionally Day 31 for 5-dose intervention] via venipuncture.
- 4) Adverse Events. Frequency of adverse events (AE) and serious adverse events (SAE) deemed related to treatment throughout the study period (Days 1-21 [1-33 for 5-dose intervention]), and at 30 days post-intervention (Day 49 [Day 61 for 5-dose intervention]).

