7.0 Study Design and Procedures

7.1 Study Design

Double-blinded, randomized, placebo-controlled pilot study to evaluate the effects of the GLP-1R agonist liraglutide treatment on drug craving in patients initiating residential treatment for OUD. In addition, the safety and feasibility of using GLP-1R agonist treatment in residential OUD patients will be established.

Study enrollment will not delay administration of standard of OUD therapies, such as behavioral treatments and/or buprenorphine/naloxone.

All participants, at the time of consent, will be enrolled in the 3-dose study procedure which takes 21 days to complete. As the vast majority of Caron patients remain in treatment for 28 days, the 3-dose procedure allows for the largest recruitment pool possible and provides a common procedure that all participants will complete. By Day 18 of the 3-dose procedure, participants will be asked whether they are able to, and willing to, continue the study for an additional 12 days (past Day 21) and receive 2 additional doses of the treatment medication (now considered the 5-dose study procedure). It is expected that not all participants will be willing or able to extend their study participation; additionally participants may either know their expected length of stay early (i.e., at admission to residential treatment) or not until close to completion of treatment. The decision to transition into the 5-dose procedure will be based on the participant's availability (i.e., whether the stay in treatment at Caron will be longer than the average 28 days) and on the participant's choice to extend their length of study participation.

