- Cardiorespiratory Function: Recordings will be collected using a portable cardiovascular autonomic cart at CaronTC. The data will be recorded via a data acquisition system (PowerLab, ADInstruments). After instrumentation, participants will rest for 10 minutes, followed by 15 minutes of continuous recordings of cardiorespiratory parameters.
 - Blood pressure, heart rate, and respiratory rate will be measured at baseline (Day 1), during study drug administration (Days 2, 8, 14, 19, 20, 26, and 31), and at the end of rebound follow-up (Day 21 [Day 33 for 5-dose intervention]). At each of these time points, participants will be placed in the supine position.
 - Blood pressure will be measured continuously using the finger volume clamp method (NOVA Finapres Medical Systems or similar) and intermittently by an oscillometric brachial artery cuff (Philips SureSigns VS3 or similar).
 - A 3-lead EKG will be used to continuously measure heart rate (Cardiocap/5 GE Healthcare or similar).
 - Respiratory rate will be measured using a pneumography belt, and oxygen saturation by pulse oximeter applied to the finger (BCI 3301 or similar).
- Cue-elicited drug craving will be evaluated. This will be evaluated using Visual Analog Scales (VAS) on Day 1 and Day 19 [and additionally at Day 31 for 5-dose intervention].
 - Cue-elicited craving will be measured on a 0-100 point VAS, where 0= no craving, 100 = maximum craving. Assessments will be taken prior to, and immediately after, exposure to visual drug cues in the Cue Response Task.
- Ecological Momentary Assessment (EMA): EMA data will be collected throughout the study (Days 1-21 [Days 1-33 for 5-dose intervention]) 4 times per day via smartphones for the first 3 days (Days 1-3) and then on a rotating "4-days on, 2-days off" schedule starting Day 6. Data to be collected include: Ambient Drug Craving; Positive and Negative Mood; Pain/Discomfort; and Sleep on 0-100 point VAS.

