18.7 Stopping Rules

Blood pressure, heart rate, and respiratory rate will be measured on Days 1, 2, 8, 14, 19, and 21. On each day, each measure will be recorded 3-4 times and then averaged. Participants will be withdrawn if they experience an average daily value for any measure on Day 1, 2, 8, 14, or 19:

- Systolic blood pressure (SBP) changes >40 mmHg, or <90 mmHg or >200 mmHg, or clinical symptoms of hypertension (e.g. headache, dizziness, blurred vision, nausea edema) or hypotension (e.g. dizziness, nausea, fainting) develop
- Heart rate reaches levels <40 beats/min or >120 beats/min
- Respiratory rate changes by >5 breaths/minute or reaches levels <10 breaths/minute or >24 breaths/minute

The medical monitor will be alerted and immediate medical assistance will be sought from the medical staff at Caron if participants experience any of these events, or more serious AEs. The investigators will also exercise discretion to end an individual's study participation if they should engage in behavior that could jeopardize their own health and well-being or that of others.

Participants who develop any new conditions described in the exclusion criteria during the treatment phase of clinical trial will be removed from the study.

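### The numeric vital-sign withdrawal limits stop at Day 19, so participants who extend to 2.4 mg and 3.0 mg have no numeric trigger on Days 20, 26 or 31

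*Combined protocol and SAP*

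**What the plan says.** Section 3.3.1 first lists the measurement days: "Blood pressure, heart rate, and respiratory rate will be measured on Days 1, 2, 8, 14, 19, and 21". It then gives the rule, "Participants will be withdrawn if they experience an average daily value for any measure on Day 1, 2, 8, 14, or 19", followed by these limits:

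- systolic pressure: a change of more than 40 mmHg, a value below 90 or above 200 mmHg, or symptoms of hyper- or hypotension;
- heart rate: below 40 or above 120 beats/min;
- respiratory rate: a change of more than 5 breaths/min, or a value below 10 or above 24.

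Section 18.7 (Stopping Rules) repeats both day lists unchanged.

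For the 5-dose course, section 7.2 requires the same vital signs "during study drug administration (Days 2, 8, 14, 19, 20, 26, and 31), and at the end of rebound follow-up". Sections 7.2.6, 7.2.8 and 7.2.9 and footnote 3 of the 5-dose schedule confirm Days 20, 26 and 31. Section 1.3 includes the two new dose-start days in the safety endpoint: "Change in respiratory from baseline (Day 1) to: i) the beginning of each study drug dose (Days 2, 8, 14, 20, 26".

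Two other provisions have no day limit. Section 3.3.1 adds: "Participants who develop any new conditions described in the exclusion criteria during the treatment phase of clinical trial will be removed from the study". The relevant exclusions are criterion 12 (serious cardiovascular disease) and criterion 17, which covers abnormal examination findings, vital signs, EKG and "safety lab values that are deemed clinically significant by study physician". Section 18.7 also calls for a medical-monitor alert "if participants experience any of these events, or more serious AEs".

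**The concern.** The day list in the rule is the 3-dose calendar without its off-drug day. Many other sections add the 5-dose days in brackets; these two do not. No reason is given for dropping the limits as the dose rises, and the text looks like a list that was not updated when the extension was added. Site staff who follow it literally would apply a mandatory numeric rule at the three lower doses and none at the two highest.

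The same reading would then be handled differently by dose. Take a respiratory rate of 14 on Day 1 and 20 later. The change is 6, above the limit of 5, while 20 lies inside the 10–24 band. (This assumes change is counted from Day 1, as in section 1.3; the rule names no reference point.) On Day 14, at 1.8 mg, withdrawal is mandatory. On Day 26, at 3.0 mg, it is not, unless a physician deems the value clinically significant. A mean heart rate of 125 gives the same contrast.

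This matters because section 1.1 makes safety over the 30-day, 5-dose titration an objective, and section 10.0 lists heart rate increase among the serious side effects. Section 7.4.6.5 has respiration and heart rate followed after every dose increase, but after the last two increases no numeric action is attached to the result.

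**Working it through.** **Inputs.** Rule days: 1, 2, 8, 14, 19 (3.3.1, 18.7). 3-dose assessment days: 1, 2, 8, 14, 19, 21. 5-dose assessment days: 1, 2, 8, 14, 19, 20, 26, 31, 33 (footnote 3 of each schedule). Doses: 0.6, 1.2, 1.8, 2.4 and 3.0 mg, six days each, Days 2–31 (7.2.2–7.2.9, 7.4.2).

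**Step 1: scheduled days outside the rule.**

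- 3-dose: Day 21 only, which is off drug.
- 5-dose: Days 20, 26, 31 and 33. Day 33 is off drug, so the uncovered on-drug days are 20, 26 and 31.

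**Step 2: coverage of on-drug assessments in the 5-dose course.**

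| Day | Dose (mg) | Numeric rule applies |
|---|---|---|
| 2 | 0.6 | yes |
| 8 | 1.2 | yes |
| 14 | 1.8 | yes |
| 19 | 1.8 | yes |
| 20 | 2.4 | no |
| 26 | 3.0 | no |
| 31 | 3.0 | no |

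That is 4 of 7 overall: 4 of 4 at 0.6–1.8 mg and 0 of 3 at 2.4–3.0 mg. For the first-day assessment of each dose, it is 3 of 3 for doses 1–3 and 0 of 2 for doses 4–5.

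**Step 3: exposure still to come after each uncovered day.** The course is 6 × (0.6 + 1.2 + 1.8 + 2.4 + 3.0) = 6 × 9.0 = 54.0 mg over 30 doses. Assume the pre-breakfast dose comes before the assessment.

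- After Day 20: Days 21–25, 5 × 2.4 = 12.0 mg; Days 26–31, 6 × 3.0 = 18.0 mg. Total 11 doses, 30.0 mg; 30.0/54.0 = 56%.
- After Day 26: Days 27–31, 5 × 3.0 = 15.0 mg. Total 5 doses; 15.0/54.0 = 28%.
- After Day 31: none.

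The protocol does not state the order. If the assessment comes first, one more dose is avoidable on each day: 12 doses (32.4 mg, 60%) from Day 20 and 6 doses (18.0 mg, 33%) from Day 26.

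**Step 4: participants affected.** Section 7.1 says only "It is expected that not all participants will be willing or able to extend their study participation". Section 8.2 implies 50 × 0.8 = 40 completers. If 10–50% extend (an assumption), that is 4–20 people, about 2–10 of them on liraglutide under 1:1 allocation.

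**Step 5: do the other provisions set a number on these days?**

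- New-conditions clause: removal is mandatory, but entry is through criterion 12 or 17, which rest on clinical judgment.
- Discretion clause: it concerns participants' behavior, not vital signs.
- Medical-monitor alert in 18.7: it refers back to events just defined by a day-limited rule, so its reach to Days 20, 26 and 31 is unclear.
- Summaries to the medical monitor at least monthly and six-monthly DSMB meetings (9.6): neither sets a limit for a given day's vital signs.

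**The case against.** The strongest reply is that this is a drafting slip with good protection behind it. The new-conditions clause is mandatory throughout treatment, and criterion 17 names blood pressure, heart rate and respiratory rate. Clearly dangerous values are those a physician is most likely to act on, and medical staff are available around the clock. An extender has already passed four numeric on-drug checks, the last on Day 19, and section 7.4.1 describes 3.0 mg as an approved dose for obesity. The respiratory example is mild. The dose percentages describe remaining exposure; they do not say how often a limit would be crossed. Section 7.1 says most patients stay 28 days, so the upper end of the extender range may be generous.

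Much of this stands. The protocol does have a stopping provision at the higher doses, the gap concerns a subgroup, and no breach rate can be derived. It does not explain why a reading that compels withdrawal at 1.8 mg should be left to judgment at 3.0 mg. Whether the omission was deliberate or accidental, staff will follow the text as written.

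Two further objections concern the remedy. Keeping the same thresholds carries over the missing reference point for change. A Day 31 trigger prevents no dose and could cost rebound data. Both are fair and are taken up under the fix. The second has a precedent: Day 19 is already a trigger on the final dosing day of the 3-dose course.

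**Conclusion.** The concern holds. In both places where the rule appears, the numeric limits lapse at the two highest doses, and the uncovered on-drug days are exactly 20, 26 and 31. On Days 20 and 26 this can change later exposure; on Day 31 it cannot. The coverage count follows directly from the protocol. The exposure figures assume the dose precedes the assessment. The head-count rests on an assumed extension rate and shows scale only. This should be fixed: it concerns participant safety in the optional extension, and neither the sample size nor the primary comparison depends on it.

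**What to change.** In both 3.3.1 and 18.7:

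1. **Measurement sentence.** After the existing list, add: *[5-dose intervention: Days 1, 2, 8, 14, 19, 20, 26, 31 and 33]*. This also removes the implication that extenders are assessed on Day 21, which their schedule does not include.
2. **Withdrawal rule.** After the existing list, add: *[and additionally Day 20, 26 or 31 for the 5-dose intervention]*, with the same thresholds. Leave the off-drug rebound assessment (Day 21 or Day 33) outside the rule, as now. This also settles that the 18.7 alert applies on the added days.

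The same amendment could state that change is counted from Day 1, if that is what is meant, and restore Day 19 to the 5-dose list in section 9.4.

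**Cost.** One wording amendment and no new assessment. An extender withdrawn on Day 20 or 26 would lose Day 31 data, including the third cue-craving measurement, but the Day 1 and Day 19 cue-craving data would already be in hand. Withdrawal on Day 31 could lose the Day 32–33 rebound data. The size of these losses cannot be estimated, because the expected number of extenders is not given.

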3.3.2 Follow-up for withdrawn subjects

Subjects will be withdrawn from the study if the study participant withdraws consent for any reason. The primary reason for the subjects' withdrawal from the study will be recorded.

Subjects who withdraw from the study may be replaced.

Subjects withdrawn due to pregnancy, adverse events (AEs), a medical emergency, or unwillingness or inability to comply with the protocol, will undergo an End of Study telephone call (30 days after the end of study treatment) unless the withdrawal is due to death or the withdrawal of consent.

3.3.3 Discontinuation of medication

Participants who decide to discontinue study medication, but who do not withdraw their consent, will be withdrawn from the study, and will cease study tasks, although their existing data will be kept in the data set. These participants may be replaced.

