7.2 Study Procedures

- Physical and Psychological Screening Procedures: The screening will include:
 - 12-lead electrocardiogram (EKG)
 - Urine pregnancy test if female with childbearing potential
 - Psychiatric assessment including: the M.I.N.I International Neuropsychiatric Interview (M.I.N.I. 7.0.2), Form 90-Drug Inventory (Form 90-DI), Hamilton Depression scale (HAM-D), State-Trait Anxiety Inventory (STAI-Y1), and Columbia Suicide Severity Rating Scale (C-SSRS)

The C-SSRS will be administrated by appropriately trained personnel. All C-SSRS scores will be reported to the Caron Treatment Center Medical Director of Research and the Director of Research. At risk participants will be immediately reported to the Directors of Research. Any participant that reports recent suicidal ideation or behavior on the screening C-SSRS will be referred for further immediate evaluation by a clinician. Clinical judgement and additional consult with the Caron Medical Director, study PI, and/or study staff will be used to further clarify if the subject is eligible to continue in the study. Participants not at risk will be reported weekly.

The Directors will refer the clinical decision to the psychology and medical team. If the patient is deemed to be suicidal, and is willing to get help, the psychology staff will utilize their typical protocol and resources to find placement in a local psychiatric facility (e.g., Philhaven, Lancaster Behavioral Health). The patient may be transported via ambulance or via Caron transportation (depending on how safe staff feels it is to transfer) to the facility for admission. In the case that the participant is uncooperative, Service Access and Management, Inc. (SAM) will be notified to assist with emergency planning. Any participant who develops active suicidal ideation with some intent to act with or without a specific plan will be discontinued from study treatment.

• **Body Weight:** Body weight will be measured daily throughout the study (Days 1-21 [Days 1-33 for 5-dose intervention]).

Blood glucose:

- Blood samples to assess changes in more long-term indices of glycemic control, such as hemoglobin A1c (HbA_{1c}) and fructosamine, will be collected prior to the first dose of study drug (Day 2) and at the end of the target dose (Day 19 [and additionally at Day 31 for 5-dose intervention]). Samples will be analyzed by Caron's clinical laboratory.

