7.2.5 Study Test Day – (Day 19)

The following **research-only** measures, all completed on Day 1, will be repeated on Day 19, regardless of intervention length (i.e., 3-dose and 5-dose interventions). Day 19 will serve as the final dose (1.8 mg) day for participants in the 3-dose intervention. For participants in the 5-dose intervention, Day 19 will be the final day at the 1.8 mg dose before moving on to the 2.4 mg dose on Day 20.

- Cardiorespiratory function will be assessed via measurement of blood pressure, heart rate, and respiratory rate as described in Section 7.2.
- Blood samples will be collected for safety laboratory tests (CBC, CMP) and for monitoring of glycemic control. Approximately 4 teaspoons of blood will be collected.
- Body weight data will be collected.

- Cue-elicited drug craving will be evaluated using VAS.
- Neurophysiology measurements will be evaluated using fNIRS during: (1) Visual cue reactivity and (2) BART.
- Collection of ambient drug craving, mood, and sleep data by EMA.
- Stress response, sleep, and activity measurements will be collected via actigraphy wristband.
- C-SSRS
- Urine pregnancy test (if applicable)
- Aes and concomitant medications will be documented.

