7.2.9 Study Test Day – (Day 31) [5-dose intervention only]

The following **research-only** measures, all completed on Day 1 and Day 19, will be repeated on Day 31.

- Cardiorespiratory function will be assessed via measurement of blood pressure, heart rate, and respiratory rate as described in Section 7.2.
- Blood samples will be collected for safety laboratory tests (CBC, CMP) and for monitoring of glycemic control. Approximately 4 teaspoons of blood will be collected.
- Body weight data will be collected.
- Cue-elicited drug craving will be evaluated using VAS.
- Neurophysiology measurements will be evaluated using fNIRS during: (1) Visual cue reactivity and (2) BART.
- Collection of ambient drug craving, mood, and sleep data by EMA.
- Stress response, sleep, and activity measurements will be collected via actigraphy wristband.
- C-SSRS
- Urine pregnancy test (if applicable)
- Aes and concomitant medications will be documented.

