7.2.11 End of Study telephone call (Day 49 [Day 61 for 5-dose intervention])

All participants will have an End of Study telephone call. This will occur 30 days (+/- 5 days) from the discontinuation of medication. Patients will be asked to self-report their body weight at the time of the call.

Schedule of Study Activities: 3-Dose Study Drug Intervention

	Enrollment/ Baseline		Intervention		Test Day (Final dose)	Off Drug	Rebound Evaluation	Equipment Return	End of Study Telephone Call**
	Day 1	Days 2-7	Days 8-13	Days 14-18	Day 19	Day 20	Day 21	Day 22	30 days +/- 5 days end of medication
Study Drug/Placebo Dose		0.6 mg	1.2 mg	1.8 mg	1.8 mg	-		-	
Informed consent	Х								
Data collected from Electronic Medical Record ¹	х								
M.I.N.I International Neuropsychiatric Interview (M.I.N.I. 7.0.2)	Х								
Form 90-Drug Inventory (Form 90-DI)	Х								
Hamilton Depression scale (HAM-D)	Х								
State-Trait Anxiety Inventory (STAI-Y1)	х								
Columbia Suicide Severity Rating Scale (C-SSRS)	Х				Х				
Body weight	Х	х	x	X	Х	х	х		X
12-lead electrocardiogram (EKG)	Х								
Pregnancy test ²	Х				Х				
Cardiorespiratory function assessment ³	Х	Х	Х	Х	Х		Х		
Blood samples for fructosamine and A1c		X ⁴			Х				
Cue-elicited drug craving ⁵	X*				х				

	Enrollment/ Baseline		Intervention		Test Day (Final dose)	Off Drug	Rebound Evaluation	Equipment Return	End of Study Telephone Call**
	Day 1	Days 2-7	Days 8-13	Days 14-18	Day 19	Day 20	Day 21	Day 22	30 days +/- 5 days end of medication
Study Drug/Placebo Dose		0.6 mg	1.2 mg	1.8 mg	1.8 mg	•		-	
Neurophysiology measurements ⁶	X*				Х				
Safety labs (CBC and CMP)					Х				
Ambient drug craving, mood, and sleep ⁷	X*	Х	Х	х	Х	Х	Х		
Actigraphy wristband ("wearable" wristband) ⁸	Х	х	х	Х	Х	Х	Х		
Concomitant medications	Х*	Х	Х	х	х	Х	х		
Adverse events	Χ*	Х	Х	Х	Х	Х	х		Х
Return of actigraphy wristband and smartphone								Х	

^{*}Performed AFTER randomization has occurred.

^{**}ALL participants, unless they withdraw consent, will have an end of study telephone call.

¹Demographics, medical history, admission diagnoses, and current medication usage.

²If female with childbearing potential, will collect results from test at admission as data for Day 1, with research-only pregnancy tests at Day 19.

³Performed on Day 1, Day 2, Day 8, Day 14, Day 19, and Day 21.

⁴Performed on Day 2 only

⁵Using Visual Analog Scales (VAS).

⁶Using fNIRS, VAS, and BART.

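### Safety monitoring: no C-SSRS is scheduled at early withdrawal, so up to 10 of 50 participants could leave with only a pre-dose suicidality score

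*Combined protocol and SAP*

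**What the plan says.** Section 7.2.1 lists the C-SSRS among the Day 1 procedures done before randomization; dosing starts on Day 2. The next one is on Day 19. The research-only "measures, all completed on Day 1, will be repeated on Day 19, regardless of intervention length" (section 7.2.5), and the C-SSRS is in that list. For the 5-dose intervention only, the "measures, all completed on Day 1 and Day 19, will be repeated on Day 31" (section 7.2.9), again including the C-SSRS. The C-SSRS rows of the two schedules of activities show no other time.

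Section 3.3.3 covers people who stop the drug voluntarily: "Participants who decide to discontinue study medication, but who do not withdraw their consent, will be withdrawn from the study, and will cease study tasks". Sections 3.3.1 and 3.3.2 describe removal and follow-up and mention no exit assessment. On the 30-day call, section 7.2.11 says "Patients will be asked to self-report their body weight at the time of the call", and the schedules add adverse events. The schedule footnote says "ALL participants, unless they withdraw consent, will have an end of study telephone call". Section 3.3.2 guarantees the call for fewer withdrawal reasons. Neither place puts the C-SSRS in it.

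Three provisions tie leaving to suicidality:

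- Removal, section 3.3.1: "Participants who develop any new conditions described in the exclusion criteria during the treatment phase of clinical trial will be removed from the study".
- Exclusion 14, section 3.2: "Suicidal ideation within the past 1 month, or history of suicide attempts within the past 1 year, unless participation is cleared by clinician assessment".
- Stopping treatment, section 7.2: "Any participant who develops active suicidal ideation with some intent to act with or without a specific plan will be discontinued from study treatment".

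Section 7.2 also sends all C-SSRS scores to the Directors of Research, at once when a participant is at risk, and the Directors pass the clinical decision to the psychology and medical team.

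**The concern.** Section 10.0 lists suicidal thoughts and behavior among the serious side effects of liraglutide, and section 7.1 says the study will establish safety in these patients. The protocol chose a structured scale for this risk and attached a referral pathway to it. The scale is given after dosing only to those who are still in the study on Day 19. A person who stops on Day 10 because of nausea, or who simply decides to stop, has been exposed to the drug and is never asked the structured questions again.

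What is at stake is individual safety and even ascertainment: stayers are asked directly, while early leavers depend on what they volunteer or what staff notice. This is a gap in safety monitoring. It does not touch the choice of analysis, because the C-SSRS is not among the outcomes in sections 1.2 to 1.4 or 9.2.

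**Working it through.** **Inputs.** 50 randomized, 20 evaluable per group and 20% attrition (section 8.2). Cue-elicited craving, the endpoint named in section 8.2, is first measured after baseline on Day 19 (sections 1.2 and 7.2). The first post-dose C-SSRS is also on Day 19 (section 7.2.5). Leavers may be replaced (sections 3.3.2 and 3.3.3).

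**The plan's own figure.** 20 × 2 / 0.8 = 50, as stated. With 20 per group and an effect size of 0.91, a two-sided two-sample t-test at 0.05 has 80.1% power, so the base of 20 per group also reproduces.

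**Number with no post-dose C-SSRS.**

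- All planned attrition before Day 19: 50 × 0.20 = 10.
- Half of it before Day 19: 10 × 0.5 = 5.
- Attrition of 10% to 30% (assumed range), all before Day 19: 50 × 0.10 = 5 to 50 × 0.30 = 15.
- Leavers replaced until 50 complete (one reading of the replacement rule): 50 / 0.8 = 62.5 randomized and 62.5 − 50 = 12.5, so 12 or 13 leavers.

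Section 8.2 does not say when the attrition occurs. Placing it before Day 19 is reasonable, since a person who drops out before Day 19 loses both the craving endpoint and the C-SSRS. It remains an inference, which is why 10 is an upper figure under the plan's own rate. 5-dose participants who leave after Day 19 have a score at 1.8 mg but none at the 2.4 mg or 3.0 mg dose.

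**Reach of an exit assessment.** Only leavers who keep consent can be asked. The protocol gives no rate of consent withdrawal. If 20% of 10 leavers withdraw consent, 10 × (1 − 0.2) = 8 can be reached; if 50% do, 10 × (1 − 0.5) = 5.

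**Timing of the call.** The call comes 30 days, give or take 5, after the last dose: at least 25 × 24 = 600 hours. Section 10.0 expects the drug to be gone in 65 hours. A C-SSRS taken at the call is therefore an off-drug reading.

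**The case against.** The strongest reply is that these participants are closely watched. They are residential patients with planned stays of at least 4 weeks (section 4.1). They have nurse-observed daily injections (section 7.4.2), in-person meetings every other day and repeated mood ratings (section 7.2), and medical staff available around the clock (section 15.4). Adverse events are recorded from first dose to 24 hours after the last dose (section 9.1) and asked about again at 30 days. The main reason for withdrawal is recorded (section 3.3.2). Stopping study tasks does not end residential care. All of this stands, and it narrows the gap. It does not replace a direct structured question, because each route needs someone to report or notice the ideation.

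It can also be said that no planned result changes. That is correct: no endpoint, sample size or test depends on the C-SSRS.

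A reader might infer more than the documents support:

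- That the planned safety comparison is biased because C-SSRS data exist only for stayers. No by-arm C-SSRS analysis is planned, so there is no such comparison to bias.
- That ideation in leavers goes wholly unrecorded. Ideation that is detected can be recorded as an adverse event or as the reason for withdrawal.
- That the statement in section 7.2 about weekly reporting of participants not at risk implies a weekly C-SSRS. It sets how often scores are passed on; the schedules show no weekly administration.

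**Conclusion.** The point holds as a modest gap in safety monitoring that is cheap to close. Participants who leave before Day 19 have only a pre-dose C-SSRS and cannot enter the C-SSRS referral pathway after dosing. The size is up to 10 of 50 if all planned attrition falls before Day 19 and about 5 if half does; replacement could raise it slightly. A flat statement that 10 of 50 will lack a score would go too far, because the protocol does not give the timing of losses. What is missed is ideation that nobody detects in people who leave for other reasons. The documents give no ideation rate, so the number of such cases cannot be estimated.

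**What to change.** In sections 3.3.1 to 3.3.3 and both schedules, give the C-SSRS on the day of stopping to anyone who stops or is removed before their next scheduled C-SSRS and has not withdrawn consent. This covers leavers before Day 19 and 5-dose leavers between Day 19 and Day 31.

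If the person has already left the site, ask it at the existing End of Study call as a clinical safety check only. Define a referral step for a positive answer, flag the reading as off-drug, and do not pool it with on-treatment readings, since completers have no C-SSRS at that time.

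If C-SSRS results are reported, state how many participants have no post-baseline score and list removals for new ideation. No statistical test is needed.

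The cost is one short interview for roughly 5 to 8 reachable leavers (fewer if fewer leave before Day 19), by personnel already trained in the scale, plus the referral step for calls. The change also needs a protocol amendment approved by the IRB and NIDA (section 18.5). Participants who finish as scheduled have nothing added.
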